Calculations. The incremental and the AUC for glucose and insulin during the OGTT are calculated according to the trapezoidal rule. Insulin secretion is calculated dividing the $AUC_{insulin}_{0-120}$ by the $AUC_{glucose}_{0-120}$ during the OGTT. The insulin secretion/insulin resistance (IS/IR) index (disposition index = DI) during OGTT is calculated as $(AUC_{insulin}_{0-120} / AUC_{glucose}_{0-120}) * \text{Matsuda index}$ (57). Insulin sensitivity during OGTT is calculated from the Matsuda index (58), and at fasting with the homeostasis model assessment (HOMA-IR). From the hyperglycemic clamp the incremental and AUC for glucose, insulin and C-peptide are also calculated according to the trapezoidal rule. Different measurements of pancreatic β -cell function will be derived from the hyperglycemic clamp: DI will be obtained as a product of insulin sensitivity (Matsuda index) and the incremental AUC for insulin and C-peptide from 0 to 15 and from 0 to 120 minutes.

Randomization and masking. Patients will be randomly assigned in a 1:1 ratio to receive linagliptin/metformin 2.5/850mg every 12 h + lifestyle modification program, or metformin 850mg every 12 h + lifestyle modification program during 6 months. Randomization will be performed using an electronic random numbers table by a Nutritionist not involved in the study. Participants and investigators involved in the patients follow-up and outcome measurements will be masked to treatment allocation during the entire study.

Interventions. i) Linagliptin + metformin + lifestyle: Patients allocated to this group will start linagliptin/metformin pills of 2.5/850mg once daily during the first month, and after that the dose will be increased to 2.5/850mg twice daily from the second month until the end of the

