study (24 months). ii) Metformin + lifestyle: Patients on this group will continue metformin pills of 850mg once daily during the first month, and increased to 850mg twice daily thereafter until the end of the study (6 months). Both groups will receive the same lifestyle implementation program based on a prescribed diet every two months seeking to reduce their body weight at least by 5-7 %, adjusting their energy requirements based on their weight every two months, and composed from 55-60 % of carbohydrates, 25-30 % fat, and 10-15 % proteins. If the patient is sedentary, he or she will be advised to start with 45 min/week of mild to moderate exercise with a specific activity according to patients preference; patients will be counseled to increase the duration and frequency or intensity of exercise every two weeks until reaching 150min/week of moderate activity or 75 min/week of intense activity. If the patient was already physically active, it will be recommended to continue like this and vary its exercise routines.

Follow-up visits and outcome. Patients will have a follow-up visit every month. Every appointment is about 30-45 minutes; medications tolerance and side effects will be recorded in every patients' visit. Nutritional and physical activity assessment according to the patient's weight will be performed by a Nutritionist every month. Monthly adherence to medications will be evaluated by pill counting; nutritional adherence and energy intake will be evaluated at 6 months by a food frequency questionnaire, and physical activity at 0 and 6 months. At basal and at 6 months patients will have an OGTT. Primary objective is to evaluate at 6 months glucose profile during OGTT, insulin secretion and pancreatic β -cell function by the OGTT DI, and regression to normoglycemia; T2D will be diagnosed and confirmed by at least two consecutive measurements of the same criteria: glycated haemoglobin ≥ 6.5 %, fasting glucose ≥ 126 mg/dl, or 2 h glucose ≥ 200 mg/dl.

Statistical analysis

The sample size calculation was based on the fact that we expected an improvement of at least 60 % on the pancreatic β -cell function and glucose profile during the OGTT in patients with the combined treatment and at least an improvement of 20% on the metformin group, based on previous reports about glucose levels and pancreatic β -cell function in prediabetic patients before and after treatment (40, 59); in order to be able to detect a minimum difference of 40 %

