between groups in the quantitative measurement of pancreatic β -cell function, and assuming an alpha error of 5% and a beta error of 20%, we require approximately 14 patients per group. The primary analysis is the comparison of the change in glucose profile during OGTT as well as measurements of pancreatic β -cell function during OGTT. Intergroup comparisons between absolute values and delta values will be performed with a t test for independent groups; intra-group comparisons will be performed using a paired t-test. Non-numerical variables will be compared between groups with the chi squared test.

Statistical analyses and graphics will be performed using SPSS Version 21.0 (SPSS Inc) and GraphPad Prism 5.0. Statistical significance is considered when p value is less than 0.05.

REFERENCES

3. DeFronzo RA. Pathogenesis of type 2 diabetes mellitus. *Med Clin North Am.* 2004 Jul;88(4):787-835, ix.
4. Ferrannini E. Insulin resistance versus beta-cell dysfunction in the pathogenesis of type 2 diabetes. *Curr Diab Rep.* 2009 Jun;9(3):188-9.
6. [name], Davalli AM, Chavez AO, Hubbard GB, Dick EJ, Majluf-Cruz A, et al. Pancreatic islet amyloidosis, beta-cell apoptosis, and alpha-cell proliferation are determinants of islet remodeling in type-2 diabetic baboons. *Proc Natl Acad Sci U S A.* 2009 Aug 18;106(33):13992-7.

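### For beta-cell function the plan does not clearly fix whether the 6-month value or the delta decides, leaves delta undefined, and adjusts no between-group test for the basal OGTT; one pre-specified ANCOVA would settle this

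*Combined protocol and SAP*

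**What the plan says.** The primary objective, under Follow-up visits and outcome, is tied to a time point: "Primary objective is to evaluate at 6 months glucose profile during OGTT, insulin secretion and pancreatic" beta-cell function by the OGTT DI. The same paragraph schedules the data: "At basal and at 6 months patients will have an OGTT".

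The Statistical analysis section describes the main comparison differently: "The primary analysis is the comparison of the change in glucose profile during OGTT as well as measurements of pancreatic" beta-cell function. The phrase about change may cover both outcomes or only the glucose profile. The test follows: "Intergroup comparisons between absolute values and delta values will be performed with a t test for independent groups". Within arms, "intra-group comparisons will be performed using a paired t-test". Significance is p below 0.05. No covariate-adjusted model is planned, and delta is not defined.

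The sample size is argued in percentages of improvement: "we expected an improvement of at least 60" percent with the combination and at least 20 percent with metformin, "in order to be able to detect a minimum difference of 40" percent between groups in beta-cell function. With alpha 5% and beta 20% this leads to about 14 per group.

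The Calculations paragraph defines the main beta-cell measure: "The insulin secretion/insulin resistance (IS/IR) index (disposition index = DI) during OGTT is calculated as" the ratio of insulin AUC to glucose AUC, multiplied by the Matsuda index.

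**The concern.** The two planned between-group tests answer the same question with different precision. The variance of a 6-month value does not depend on its correlation r with the basal value. The variance of a delta is 2(1−r) times as large, so the delta is noisier below r=0.5 and more precise above it. With 14 per group the two will often fall on opposite sides of 0.05. If neither is named in advance for the outcome that sized the trial, the choice can settle the main beta-cell result.

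The scale adds a second open choice. The planned effect is a percentage, so delta could be absolute or percent, and DI, as a product of ratios, may well be skewed.

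Naming one t test would end the ambiguity, but without knowing r the sponsor could name the weaker one. A covariate-adjusted comparison avoids that risk, and the measurement it needs is already scheduled.

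**Working it through.** **The plan's figure.** The 14 per group cannot be reproduced, because no SD is stated. Solving backwards with a two-sided 5% t test on 26 df and 80% power gives a standardised difference d = 1.10. A 40-point difference then needs an SD of 40/1.10 = 36.4 on the same scale. The documents do not say whether that scale is the 6-month value, the delta or the percent change.

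**Inputs.** From the documents: 14 per group, 1:1 allocation, alpha 5%, power 80%, improvements of 60% and 20%. Assumed: two-sided testing, equal variances, and r from 0 to 0.9.

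**Normal data.** Let σ be the SD at one visit, and set the delta test at 80% power.
- Delta test: d = 1.10, 26 df.
- 6-month value: d = 1.10·√(2(1−r)), 26 df.
- ANCOVA: d = 1.10·√(2(1−r)) / √((1−r²)·25/24), 25 df. The factor 25/24 allows for chance imbalance in the basal value.

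At r=0.5 the 6-month d is 1.10·√1 = 1.10 and the ANCOVA d is 1.10/√(0.75·25/24) = 1.245. At r=0.7 they are 1.10·√0.6 = 0.852 and 0.852/√(0.51·25/24) = 1.169. The power figures agree with simulation; the disagreement rates come from simulation.

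| r | Delta | 6-month value | ANCOVA | The t tests disagree |
|---|---|---|---|---|
| 0.2 | 80% | 94% | 94% | 18% |
| 0.5 | 80% | 80% | 89% | 23% |
| 0.7 | 80% | 58% | 84% | 37% |
| 0.9 | 80% | 24% | 80% | 62% |

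Naming the weaker t test costs 94−80 = 14 points against ANCOVA at r=0.2 (the delta) and 84−58 = 26 points at r=0.7 (the 6-month value). ANCOVA gains most over the better t test at r=0.5, 89−80 = 9 points. It gains nothing over the delta at r=0.9. With the 6-month test at 80%, ANCOVA has 78%, 79% and 80% at r=0, 0.1 and 0.2, so it loses up to 2 points there. Its simulated type I error is about 5%.

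**Degree of freedom.** Going from 26 to 25 df moves the critical t from 2.056 to 2.060, and power from 80.0% to 79.9% if adjustment reduces no variance.

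**Why ANCOVA removes one choice.** Write Y for the 6-month value, B for the basal value and T for treatment. If Y = a + τT + bB + error, then Y − B = a + τT + (b−1)B + error. The treatment coefficient, its standard error and its p-value are identical. This holds for the absolute change on a given scale, not for percent change.

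**Scale of DI.** Applying the plan's factors of 1.6 and 1.2:
- Lognormal DI, absolute-delta test set at 80%, r = 0.2/0.5/0.7/0.9: log ANCOVA has 88/83/82/90%. Over r from 0 to 0.9 it is −1 to +3 points against the best of the three t tests (6-month value, absolute delta, percent delta).
- Lognormal DI at r=0.9: raw ANCOVA has 83% against 89% for the percent-change test, or 71% against 80% when the percent-change test is set at 80%. That is a loss of 6 to 9 points.
- Symmetric DI with SD proportional to its mean, r=0.7: log ANCOVA has 81% against 91% for the delta at CV 0.3, and 48% against 71% at CV 0.4. Raw ANCOVA stays within −2 to +1 points of the best t test.

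**Log-scale target.** The planned effect becomes 1.6/1.2 = 1.33, with ln 1.333 = 0.288. With residual log SD 0.255, d = 0.288/0.255/√(25/24) = 1.105, which gives 80% power on 25 df.

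**The case against.** The strongest reply is that the plan already answers the question. Its primary-analysis sentence speaks of change, improvement from before to after treatment is a change, and the 6-month wording can be read as a time point only. The t test on the delta is valid in a randomised trial, so one sentence naming it would suffice. Much of this stands. The reading is reasonable, and for the glucose profile change is named outright. But the beta-cell wording can also be read the other way, delta stays undefined on either reading, and a named delta test still gives up power at low and moderate r.

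It can also be said that every power figure is back-solved, since the documents give neither an SD nor r, and that ANCOVA on the wrong scale can do worse than the plan. Both are true. The second is why the scale needs a rule in advance and why a log analysis should not be required without one.

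Two stronger inferences are tempting. A reader might infer that no planned test uses the basal OGTT. That is false: the delta test subtracts it and the paired test compares with it. A reader might also infer a type I error of about 8–10% for this outcome. Simulation gives that only if success is claimed when either t test is significant, and the plan states no such rule.

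**Conclusion.** The point holds in limited form. For beta-cell function the deciding quantity is not clearly fixed, delta is undefined, and no between-group comparison adjusts for the basal value as a covariate. None of this makes the planned tests invalid, and an inflated error rate cannot be read from the text. The consequence is an open choice between tests that, under the normal model with the delta test at 80% power, disagree in 18% to 62% of trials for r from 0.2 to 0.9.

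ANCOVA is the safer deciding test when r is unknown: about 2 points below to 9 points above the better t test on normal data. That advantage depends on scale and is not guaranteed for DI. The change should be made, but the trial's validity does not hang on it. Multiplicity across the several primary outcomes is a separate matter that this does not settle.

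**What to change.** 1. For each continuous OGTT outcome, name one ANCOVA as the deciding test: 6-month value on treatment and that outcome's basal value, reported as an adjusted difference with 95% CI.
2. Say whether delta is absolute or percent, and make the t tests on 6-month values and deltas supportive.
3. Fix the DI scale before any 6-month value is seen. It may be raw, or log with the effect restated as a ratio of 1.33 and the sample-size basis restated: n=14 then has 80% power only if the residual SD of log DI is at most about 0.255. If the scale is to be chosen from basal DI pooled over arms, write the decision rule in advance, including what follows if the check fails.

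The cost is one degree of freedom, some analysis-plan wording and, if the log scale is used, a rewritten sample-size paragraph. No new data are needed. The remaining risk is a wrong scale: about 10 to 20 points or slightly more for log ANCOVA against the delta test if DI is symmetric with CV 0.3–0.4, and 6 to 9 points for raw ANCOVA against a percent-change test if DI is lognormal with r=0.9.
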